A High Density EEG Comparison of Sleep, Sleep Initiation and Arousal Patterns in Insomnia Patients and Normal Controls

Principle Investigator: [name], PhD

Co-Investigators: [name]

[name]

Institutional Affiliation: University of Wisconsin-Madison

Protocol Version: 9/8/2015

Funding Sponsor: MERCK Sharp and Dohme Corporation

1. Project Summary

Insomnia, defined as a subjective report of difficulty initiating sleep, maintaining sleep, and/or non-restorative sleep, leads to significant daytime dysfunction and increased health risks. A commonly held hypothesis is that insomnia is caused by a state of hyperarousal, but the neurobiological mechanisms of hyperarousal in insomnia are poorly understood, in part because of limitations in our ability to image the brain during normal human sleep with sufficient temporal resolution. Insomnia is particularly prevalent among depressed individuals, yet little is known about whether this same state of hyperarousal is present in comorbid depression and insomnia. Furthermore, the efficacy of insomnia treatment is judged by subjective report of the patient and demonstration of changes in sleep latency and/or sleep amount which are generally small in magnitude; there are currently no data to demonstrate that insomnia treatments correct any functional abnormalities in the sleep process that likely contribute to neurobehavioral abnormalities and health risks. The goals of the proposed study are to use hdEEG to define abnormalities in specific aspects of sleep in insomnia patients with and without depression compared to healthy sleeping control subjects to define biomarkers that will both increase our understanding of the pathophysiology of insomnia as well as provide targets to assess treatments for insomnia.

2. Background and Significance

2.1 Overview

Insomnia is the most common sleep disorder (Ohayon 2002), with at least 10% of the general population suffering from chronic insomnia severe enough to impact adversely on health and quality of life (Benza 2005, Roth et al 2001). When combined, the high prevalence rate, daytime impairments, and other adverse effects of insomnia on the outcomes of comorbid psychiatric or medical conditions push estimates of the direct and indirect costs of chronic insomnia up to tens of billions of dollars annually (NIH 2005). There is mounting evidence that insomnia contributes to increased risk for development of hypertension and diabetes (Vgontzas et al 2013), heart failure and overall mortality (Laugsand et al 2013), and mood disorders (Baglioni et al 2011, Suh et al 2013). Currently, insomnia is a clinical diagnosis based on subjective complaints about quantity and/or quality of sleep that result in daytime impairment. Symptoms include difficulty initiating sleep, difficulty maintaining sleep, waking up too early, and sleep that is often described as “non-refreshing” or “non-restorative”. The pathophysiology of insomnia is poorly understood and there are no objective diagnostic measures currently in existence. The evaluation of treatment options, including behavioral therapy and pharmacotherapy, also suffers from the lack of an objective measure of sleep efficacy, relying instead on traditional objective measures of sleep quantity and/or subjective reports of sleep quality (NIH 2005).

2.2 Examining cortical sources of abnormal activity during sleep in insomnia with hdEEG

One of the most common theories of insomnia is focused on the idea of hyperarousal (for a review see (Riemann et al 2010)). Although there is support for this theory from a wide range of fields, including physiological and neuroendocrine studies, the majority of evidence comes from either electroencephalographic (EEG) or neuroimaging investigations. Several studies have reported increases in higher frequency EEG activity (i.e. beta and gamma bands) during various stages of sleep (Buysse et al 2008, Freedman 1986, Krystal et al 2002, Merica et al 1998, Perlis et al 2001a, Perlis et al 2001b) suggestive of an aroused brain. Unfortunately, all of these studies derived their results based on the few EEG channels typically included in a routine sleep laboratory polysomnography (PSG), making it impossible to determine if the increase in high frequencies was ubiquitous across the whole brain or whether certain cortical areas were more aroused than others. The seminal work of Nofzinger et al. (Nofzinger et al 2004) using positron emission tomography (PET) provided the first direct evidence of regional hyperarousal in insomnia, showing that the attenuated decline of metabolism, although global, was highest in several cortical regions, including the insular cortex, anterior cingulate, and prefrontal cortices. However, although PET imaging provides increased spatial resolution over limited channel EEG, it provides a limited imaging window (approximately 20 minutes) that cannot provide temporal information across an entire night of sleep or examine the processes sleep initiation or arousal with sufficient temporal resolution. An earlier study using single photon emission tomography (SPECT), instead showed decreased blood flow (i.e. decreased activity) across all regions of interest (including frontal medial and lateral cortices) around the time of sleep onset (Smith et al 2002).

[figure not shown]

Figure 1: Slow wave hot spots in normal subjects. Cortical flat map showing slow wave involvement (grand average current around the negative peak of the slow waves - approx 100 waves/subject for 6 subjects - expressed as a ratio of the baseline current during eyes closed waking. Several involvement hot spots overlap with areas of hyperactivity in insomnia patients including the anterior cingulate, the left inferior frontal gyrus and insula. Modified from Murphy et al. 2010

and 3) is conducive to examining sleep.

Recent advances in electroencephalographic recording techniques have produced new ways to probe the process and function of sleep. Through the use of high-density EEG (hdEEG, 256 channels), we are able to approach the spatial resolution of other brain imaging modalities while affording the millisecond temporal resolution of EEG and providing a direct measure of the underlying brain activity, unlike the indirect and/or secondary biophysical signals of brain hemodynamics/metabolism obtained with PET or fMRI that are suboptimal for exploring the short-lived spatio-temporal dynamics of many brain processes. While most EEG analysis is

Most likely these conflicting results are related to limited time imaging windows (both during sleep onset, but SPECT integrating only over several minutes). What is needed is to explore the role of hyperarousal in insomnia as an imaging tool that is able to 1) resolve temporally whether hyperarousal is constant, fluctuates based on the ongoing pattern of EEG, or is a specific, abnormal reaction to incoming stimuli; 2) resolve spatially the difference between global and regional cortical arousal; and 3) is conducive to examining sleep.

performed using scalp voltages, the use of hdEEG provides sufficient data to accurately model the cortical sources of scalp electrical activity. Our group at UW has developed hdEEG in sleep as a neuroimaging tool and demonstrated its utility for studying the role of sleep in normal brain function. For example, we have shown that both slow waves and spindles, characteristic sleep EEG waveforms, are useful measures of localized brain activity. HdEEG has revealed that sleep is more intense (more slow wave activity, EEG power between 0.5 – 4 Hz) in the cortical regions that learn the most during waking, thus demonstrating that not only do slow waves reflect sleep intensity, but they also reflect the underlying the cellular need for sleep in a regionally specific manner (Huber et al 2007, Huber et al 2006, Huber et al 2004, Huber et al 2008, Matta et al 2010, Sarasso et al 2010). Additionally, sleep slow waves have been shown to travel across the cortical mantle from distinct origins (Massimini et al 2004). Notably, the cortical hot spots for slow wave origination and propagation include the insula and the anterior cingulate, PET-identified regions of hyperactivation in insomnia (Murphy et al 2009)(Figure 1).

We have extensive experience using hdEEG technology to study brain activity and sleep abnormalities in various neuropsychiatric conditions, including insomnia. We have identified sleep spindle abnormalities in schizophrenia, which have been suggested to have an etiopathologic role in the disorder and may be one of the most specific biomarkers for the disorder (Ferrarelli et al 2007, Ferrarelli et al 2010). In depression, we have found evidence for abnormalities in sleep homeostasis through analyses of brain activity during sleep and wakefulness prior to and following nocturnal sleep (Goldstein et al 2012, Plante et al 2013b) as well as a regionally specific decrease in slow waves in hypersomnolent depressives (Plante et al 2012b). Our preliminary work in insomnia under previously approved protocols H-2007-0150, and continuing with H-2009-0019, (comparing 9 subjects with primary insomnia, 9 age- and sex-matched depressives and 9 matched healthy sleepers, Table 1) revealed that beta and gamma activity were increased globally in both insomnia and depression in comparison to controls, but only alpha activity, particularly in deeper sleep (stage N3) distinguished primary insomnia from depressed and control subjects. Notably, when localized in the cortex, these increases in alpha during N3 sleep were most prominent in primary sensory and associative cortices (including somatosensory, auditory and visual cortices), suggesting that even during the deepest stage of sleep, sensory areas are still relatively active in insomnia relative to controls (Figure 2). Our primary aim, then, would be to extend and confirm this result in a larger group of primary insomnia participants in

	PI (N= 9)		MDD (N= 9)		GSC (N= 9)		Overall ANOVA			t tests (uncorrected)		
	Sex (m/f)		Sex (m/f)		Sex (m/f)		df	F	p	1 vs. 2	1 vs. 3	2 vs. 3
Age (years)	3/6		3/6		3/6		—	—	—	—	—	—
HRSD-17	5.56 (2.07)		16.00 (4.54)		—		—	—	—	—	—	—
ISI	17.67 (3.81)		—		—		—	—	—	—	—	—
ESS	6.11 (4.01)		—		—		—	—	—	—	—	—
TST (min)	361.89 (45.06)		384.33 (48.52)		386.22 (38.07)		2,24	0.85	.441	—	—	—
WASO (min)	86.89 (29.68)		45.17 (24.33)		23.39 (23.30)		2,24	13.94	< .001	.007	< .001	.262
AI (#/hr.)	11.96 (5.47)		11.11 (7.66)		9.43 (9.86)		2,24	0.24	.789	—	—	—
SE (%)	79.07 (6.40)		86.06 (5.82)		92.61 (5.53)		2,24	11.76	< .001	.059	< .001	.083
SOL (min)	8.67 (8.76)		17.28 (17.89)		7.94 (8.99)		2,24	1.52	.238	—	—	—
N1 (%)	12.54 (5.39)		9.36 (7.13)		7.24 (3.48)		2,24	2.09	.146	—	—	—
N2 (%)	64.37 (7.43)		60.24 (9.19)		59.67 (9.20)		2,24	0.79	.465	—	—	—
N3 (%)	8.63 (6.71)		10.64 (12.15)		14.77 (9.66)		2,24	0.92	.411	—	—	—
REM (%)	14.44 (5.71)		19.76 (6.64)		18.32 (4.85)		2,24	2.03	.153	—	—	—
REML (min)	107.72 (30.43)		97.44 (46.66)		101.72 (18.92)		2,24	0.21	.814	—	—	—

Table 1: Comparison between insomnia (PI) and good sleep control (GSC) subjects on sleep and demographic measures. HRSD = Hamilton Depression Rating. ISI = insomnia severity index. ESS = Epworth Sleepiness Scale. TST = Total sleep time. WASO = Wake after sleep onset. AI = Arousal index. SE = Sleep efficiency. SOL = Sleep onset latency. REML = REM latency. % expressed relative to TST. Modified from Goldstein APSS 2013.

[figure not shown]

Figure 2: Increased cortical alpha during deeper sleep in insomnia patients. Cortical flat map showing areas with significantly increased alpha (8 – 12 Hz) activity when comparing insomnia patients to good sleeping controls (SnPM cluster test, t-threshold based on $\alpha < 0.05$, 1000 permutations, 9 subjects per group). 5 minutes of NREM sleep selected from the middle of the 1st NREM episode cycle (including N3 in all but 1 insomnia patient) was band-pass filtered prior to source localization (Geosource, 4-shell head model, minimum norm solution with sLORETA constraint, tikhonov regularization -1).

order to increase our localization power, to see whether this increase persists throughout the night during normal sleep, or is specific to stage N3, and to determine if it is particularly associated with sleep onset and/or sleep maintenance difficulties; we will also examine how this finding relates to the process of falling into and arousing from sleep.

2.3 Defining abnormal activity during sleep transitions in insomnia with hdEEG

[figure not shown]

Figure 3: The relative involvement of sensory brain regions in slow waves progressively increase during the descent into sleep.
 Cortical flat map shows significantly different slow wave involvement (based on the Wilcoxon Signed rank test, 6 subjects) when comparing the early (2-3, red) to late (8-9, blue) falling asleep periods. To compare results obtained in different epochs and subjects, relative involvement is computed as the ratio between the value in each voxel and the value resulting from the average of all brain voxels. Modified from Siclari et al. *in preparation*.

subjects to systematically wake them up throughout the night) in a group of normal subjects to describe how different waveforms contribute to falling asleep in a regionally specific manner by examining hdEEG during equally distributed time periods between the end of posterior alpha (10-20 channel Oz) and the first slow wave burst (2 consecutive slow waves without an arousal (Siclari et al. *in preparation*). In good sleeping controls, slow waves followed two spatially and temporally distinct processes during the transition from wakefulness to sleep. The early process was characterized by isolated, large amplitude slow waves that involved mainly the frontal regions and was associated with high gamma power. The late process was marked by numerous smaller slow waves that tended to originate more diffusely over the cortex, and to involve also the temporal, lateral parietal and occipital brain regions. The falling asleep process is thus characterized by a transition from predominantly local to increasingly global sleep patterns. This process may be disrupted in insomnia, particularly given the similarities between areas from which slow waves involved only later in the falling asleep process originate and areas exhibiting alpha activity during deep NREM sleep in insomnia patients.

Certainly sleep initiation is not the only potential problem in people with insomnia; frequent awakenings during the night are commonly reported by many patients. However, there is surprisingly little literature examining the response of insomnia subjects to arousing stimuli. Limited channel event related potential studies during sleep seem to support the theory of hyperarousal in insomnia subjects, especially during the sleep onset period (Bastien et al 2008, Devoto et al 2005, Spiegelhalder et al 2012, Yang & Lo 2007), despite similar auditory arousal thresholds as controls (Mendelson et al 1986). However, without the ability to localize the

Recently we have begun to use hdEEG to examine the process of falling asleep in normal subjects. Although it has long been recognized that falling asleep involves a process developing over time (for instance see Hori's nine-stage system and EEG waveforms, (Hori et al 1994), how this process develops across the cortex is just now being elucidated. We recently demonstrated that cortical areas that have been overly taxed during the day may go offline even while the rest of the cortex remains awake (Hung et al 2013). Moreover, we have used serial awakenings (repeatedly presenting stimuli to

Insomnia and Sleep Patterns Study

cortical sources of the brain's response to such stimulation, it is difficult to draw strong conclusions. We now know from other imaging techniques as well as from our own work with hdEEG that external stimuli do reach the cortex even during the deepest stages of sleep (Dang-Vu et al 2011, Riedner et al 2011). The degree to which such stimuli could be locally arousing the cortex is unknown, and it is likely that insomnia patients may show different patterns of reactivity than healthy sleepers.

In summary, the use of hdEEG to study sleep in insomnia with and without depression affords a unique opportunity to image the brain with exquisite temporal resolution throughout the sleep period. Not only can we study the spatial and temporal dynamics of sleep throughout the night, but we can also examine the processes of falling asleep and arousing from sleep; these critical events are likely to be particularly important for understanding insomnia, since they reflect the primary complaints of insomnia patients—difficulty falling asleep and difficulty maintaining sleep. No other currently available imaging technique is capable of providing functional imaging data throughout the sleep process or in individuals who can sleep without restriction of their normal nocturnal movement. Furthermore, in contrast to other imaging procedures, hdEEG is relatively inexpensive, portable, and can be performed repeatedly making it ideal for longitudinal studies. Our preliminary data in a small number of subjects already shows significant differences in topographic patterns of sleep EEG activity in comparison not only to healthy sleepers but also depressed subjects, suggesting that the technique will be able to detect abnormalities in brain activity patterns that are specific for insomnia. Even more importantly, we can localize one of these insomnia-specific abnormalities, increases in alpha activity during deep stages of sleep, to sensory areas of the cortex, strongly suggesting that these specific areas remain relatively activated during sleep. The proposed study will provide novel data regarding mechanisms of insomnia and will be used to design future studies that will assess the effects of insomnia treatments on patterns of abnormal brain activity. The identification of specific abnormalities during sleep as well as in the processes of falling asleep or arousing from sleep will potentially allow us to distinguish the effects of pharmacologic treatments that promote sleep through different mechanisms, such as by increasing GABA transmission, blocking histamine receptors or blocking orexin receptors.

3. Specific Aims

3.1. Primary Objectives:

1. Examine differences in the cortical sources of sleep waveforms in insomnia patients with and without depression compared to healthy sleeping controls.
2. Define cortical source abnormalities in the processes of falling asleep and arousing from sleep in insomnia patients with and without depression compared to healthy sleeping controls.

3.2 Secondary Objectives:

1. Correlate abnormalities in sleep EEG patterns with specific insomnia symptoms, including sleep onset difficulties, sleep maintenance problems, nonrestorative sleep and daytime dysfunction.

Insomnia and Sleep Patterns Study

2. Define abnormalities in overnight changes in waking EEG activity in insomnia patients with and without depression compared to healthy sleeping controls.
3. Explore whether abnormalities in sleep and waking EEG activity in insomnia patients, with and without depression, normalize following treatment with a sleep medication.

3.3 Clinical Hypotheses:

1. Insomnia patients will show increased regional EEG alpha activity in sensory cortical areas particularly during sleep.
2. Insomnia patients will show abnormalities in the process of sleep initiation, including regional sources of high frequency EEG activity that will interfere with the normal progression of the sleep process.
3. Insomnia patients will show abnormalities in the regional patterns of cortical arousal responses to external stimuli during sleep, particularly in the sensory cortical areas exhibiting increased alpha activity.
4. Abnormalities in sleep EEG patterns may be correlated with specific insomnia symptoms, particularly difficulty with sleep initiation or maintenance.
5. Waking EEG in insomnia patients will not show overnight recovery compared to controls, which will be correlated with specific EEG abnormalities during sleep, such as elevations in higher frequency activity.
6. Explore whether insomnia patients with and without depression differ in abnormalities in sleep EEG patterns.

4. Research Design and Methods

4.1 Study Population

Studies will be carried out in 20 individuals with insomnia, 20 individuals with depression and insomnia, and 20 age- and sex-matched healthy controls (women and men aged 18-45 years who are English speaking). We will ensure that our sample includes individuals with both sleep onset and maintenance issues, and that at least 1/3 of the sample is male. Strict inclusion/exclusion criteria will be applied to the sample to reduce the variability of the data and avoid confounding factors.

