4.4 Statistical Considerations

4.4.1 Sample Size Justification

The strength of this study design is that it will allow us to characterize the cortical activity of insomnia patients with a unique combination of temporal and spatial resolution during sleep initiation, normal sleep, and awakening from sleep. As such, a number of the questions that can be addressed with this design are highly novel for which there is little direct evidence on which to base sample size calculations. However, the substantial pilot data collected from a population of insomnia patients as well as age- and sex- matched controls for one of the primary hypotheses (2.7.2a) allows us to confidently support our proposed choice of sample size. The Cohen's *d* effect size averaged across the significant source cluster was 1.15. Our power to detect an effect of this magnitude in our proposed final sample size of 20 per group using an alpha level of *p*=.05, 2-tailed would be approximately 94%. Our power to detect the difference between potential subgroups of sleep maintenance versus sleep onset with the insomnia group alone (10 per group) would be approximately 68%. Furthermore, on the basis of other similar analyses with relatively small sample sizes (e.g. - <20 subjects per group) examining local sleep homeostasis (Huber et al 2004), the traveling phenomena of slow waves (Massimini et al 2004),

the cortical localization of evoked K-complex slow waves (Riedner et al 2011), slow wave reduction in hypersomnolent depressives (Plante et al 2012b), sleep spindle reductions in schizophrenia (Ferrarelli et al 2007, Ferrarelli et al 2010), the current study design should provide us with adequate statistical power.

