order of minutes instead of hours. Preliminary results suggest that tonic alpha power during N3 sleep may distinguish between these groups, but it is also conceivable that events like slow waves or spindles may provide additional distinguishing information, and windows around these events may be relevant. The **outcome measure** addressing **this first primary study objective** will be the cortical localization maps of band-pass filtered EEG data in the frequency range of interest (identified by the scalp-level analysis from the initial steps, e.g. alpha) using a distributed inverse solution (i.e. LORETA, for details of the methods involved see (Murphy et al 2011)). All group comparisons of distributed source localization maps will be analyzed using statistical nonparametric mapping (SnPM)(Nichols & Holmes 2002) which is ideally suited to address the multiple comparison issues inherent to neuroimaging and which does not make unwarranted assumptions about data distribution. This method has been successfully applied in a number of hdEEG studies in our laboratory (Ferrarelli et al 2007, Huber et al 2006, Huber et al 2004), and compares favorably with Statistical Parametric Mapping for analyses having low degrees of freedom.

Falling asleep imaging (Primary Objective 2a)

During both the baseline and serial awakening sleep nights, the descent into (or back into) sleep will be analyzed by dividing the interval between the last appearance of occipital alpha and the first instance of a burst of slow waves (more than 2 slow waves consecutively without an arousal) into 10 equally spaced temporal bins prior to cortical source estimation. Distributed source localization maps for individual frequency ranges will then be average within subject and then within group prior to statistical analysis.

Sleep arousal imaging (Primary Objective 2b)

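### Controls are matched on age and sex, but the group comparisons name no age, sex or matched-set term: mildly conservative where matching works, uncorrected where no matching is stated

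*Combined protocol and SAP*

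**What the plan says.** Section 4.1 sets the sample as "20 individuals with insomnia, 20 individuals with depression and insomnia, and 20 age- and sex-matched healthy controls" and requires that "at least 1/3 of the sample is male". For the "20 age- and sex-matched healthy controls", it does not say whether matching is by individual or by group, which patient group the controls are matched to, or how close in age a match must be.

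Section 4.4.2 states that "All group comparisons of distributed source localization maps will be analyzed using statistical nonparametric mapping". No covariate, paired statistic or restricted permutation is named there. The same holds for the ANOVAs across frequency bands and the repeated-measures ANOVAs for behavioural and sleep-architecture data.

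Section 4.4.1 bases power on "our proposed final sample size of 20 per group" and on a pilot in which the "effect size averaged across the significant source cluster was 1.15". It describes that pilot as "substantial pilot data collected from a population of insomnia patients as well as age- and sex- matched controls". Section 2.2 gives the pilot's make-up: nine people with primary insomnia, "9 age- and sex-matched depressives and 9 matched healthy sleepers".

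**The concern.** Matching on variables that predict the outcome removes their share from the true variance of the group difference. An independent-group standard error, or a permutation that shuffles labels freely across all participants, keeps that share in. The test then rejects too rarely under the null and has less power than a test that uses the matching variables.

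The opposite situation arises where groups are not matched. Hypothesis 6 in section 3.3 compares insomnia with and without depression, and section 4.4.1 considers onset against maintenance subgroups of 10. Neither pair is stated to be matched. If age or sex differs between them, the difference enters the EEG contrast uncorrected.

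These are two separate issues and apply to different comparisons. Conservatism needs matching to have worked; uncorrected imbalance needs it to be absent or to have failed. What is at stake is some efficiency in the first case and interpretability in the second.

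**Working it through.** **Inputs from the documents.** 20 per group, or 10 per insomnia subgroup; d = 1.15; two-sided alpha 0.05; stated power about 94% and 68% (section 4.4.1). At least one third male (section 4.1).

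**Assumptions.** The documents give neither the variance share R² explained by age and sex nor a within-pair correlation ρ. I use 0.1, 0.2 and 0.3 for each, with ρ = R² representing exact matching. The smaller effect d = 0.8 is also mine. It is shown because 1.15 was averaged over a cluster selected as significant in a pilot of nine per group, so the true effect may be smaller. Effects are in units of the total SD.

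**1. The plan's own figures.** Independent two-sample t test, noncentrality d√(n/2), df = 2n − 2.
- n = 20: 1.15 × √10 = 3.64, df 38, power 94.3%.
- n = 10: 1.15 × √5 = 2.57, df 18, power 68.2%.

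Both stated figures reproduce.

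**2. Type I error when matching works but is ignored.** The true variance of the mean difference is 2σ²(1 − ρ)/n, while the unadjusted test uses about 2σ²/n. The standard error is therefore too large by a factor 1/√(1 − ρ). In large samples the type I error is 2[1 − Φ(1.96/√(1 − ρ))].

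| ρ | SE overstated by | Formula | Simulated t test, n = 20 |
|---|---|---|---|
| 0.1 | 5.4% | 3.9% | 3.9% |
| 0.2 | 11.8% | 2.8% | 2.9% |
| 0.3 | 19.5% | 1.9% | 2.1% |

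A maximum-statistic permutation test with free label shuffling (50 correlated sources, 1,000 simulated datasets) gave family-wise error of 4.9% at ρ = 0, 3.0% at 0.1 and 1.3% at 0.3. The direction is the same for the plan's method.

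**3. Power, 20 per group.** Unadjusted: simulated on matched sets, so that the baseline already has the benefit of matching. Adjusted: ANCOVA with effect d/√(1 − R²) and df 36.

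| R² = ρ | d = 1.15 unadjusted | adjusted | d = 0.8 unadjusted | adjusted |
|---|---|---|---|---|
| 0.1 | 95.0% | 96.2% | 69.9% | 73.7% |
| 0.2 | 96.1% | 97.7% | 71.2% | 78.6% |
| 0.3 | 96.9% | 98.8% | 72.2% | 83.7% |

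The gain is about 1 to 2 points at the planned effect and about 4 to 12 points at d = 0.8.

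**4. Cost if age and sex explain nothing.** With R² = 0 and d = 1.15, losing two degrees of freedom takes power from 94.33% to 94.27% at 20 per group, and from 68.2% to 67.5% at 10 per group.

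**5. Comparisons not stated to be matched.** Taking one third male in each group, the standard error of a chance difference in proportion male is √(2 × ⅓ × ⅔ / n). This is 0.15 at n = 20 and 0.21 at n = 10. A sex effect of s SD on the measure would shift the group contrast by s times the actual difference in proportion male. The size of s is not documented. A systematic difference, for example a different sex mix among depressed participants, would add bias that does not shrink with n.

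**The case against.** The strongest reply is that little is lost. A conservative test does not threaten validity, and 1 to 2 points of power at the planned effect is small. No document gives an R²: the support is three reference titles on sex differences in sleep EEG, and none speaks to age. The eligible age range is narrow, which limits what age can explain. SnPM does not exclude covariates, so silence is not a decision against them, and section 4.4.2 says analyses will be planned with a biostatistics group. Covariates also bring in a linear model at every source, although SnPM was chosen partly to avoid distributional assumptions. All of this stands, and it keeps the point minor.

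It does not remove the point. The same section promises analyses fixed in advance, and adjustment decided after the maps are seen would add analyst discretion in a study that is already largely exploratory.

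A reader might infer three stronger claims that the documents do not support:
- **One control group cannot be closely matched to both patient groups.** The pilot matched three groups, so it can be done. The plan simply does not say whether it will be.
- **The 94% power is overstated.** It is not. Where matching works, the unadjusted test has at least that power.
- **Adjustment raises power from 94% or 69%.** Those are the figures for unmatched groups. With effective matching the unadjusted test already starts at 95-97% or 70-72%.

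**Conclusion.** The omission is real and its consequence modest. In the patient-control comparisons, if matching is achieved and age and sex predict the measure, the unadjusted test runs at about 4%, 3% or 2% in place of 5% and gives up 1 to 2 points of power at d = 1.15. The loss is larger at the assumed d = 0.8. If age and sex explain nothing, nothing is lost. In the comparisons not stated to be matched, the concern is uncorrected chance or systematic imbalance, whose size cannot be computed from the documents; no actual imbalance is shown. Severity is minor. Confidence is moderate, because every magnitude rests on an assumed R² or correlation.

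**What to change.** In section 4.4.2, prespecify age and sex as covariates in the SnPM group comparisons, permuting residuals by the Freedman-Lane method, and in the ANOVAs. If matching is by individual set, permuting labels within matched sets is the direct alternative for the patient-control comparisons; the unmatched comparisons would still need the covariates. Keep the unadjusted map as a sensitivity analysis.

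In section 4.1, state whether matching is by individual or by group, to which patient group or groups, and with what age tolerance. Sections 4.1 and 4.1.2 also give different upper age limits (45 and 40). They must be reconciled, since they set the range over which age is matched.

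The cost is two degrees of freedom (about 0.1 point of power at 20 per group and under 1 point at 10 per group if the covariates explain nothing), a linear-model assumption at each source, and a permutation test that is approximate rather than exact. No new data or participants are needed.
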